Hypoglycemic Events that did not result in Serious Adverse Event	Can repeat session
PI initiated discontinuation of study due to patient or equipment concerns	Can repeat session
Serious or Unanticipated Adverse Event deemed related to the study	Unable to repeat session

Table 1: Repeat Session Table

SAFETY MONITORING

Adverse Events, Unanticipated Problems, Protocol Violations and Data Breaches

Reporting of events are noted below:

Type of Event	To whom will it be reported:	Time Frame for Reporting	How reported?
Any internal event resulting in death that is deemed DEFINITELY related to (caused by) study participation (Note: An internal event is one that occurs in a subject enrolled in a UVa protocol.)	IRB-HSR	Within 24 hours	IRB Online and phone call www.irb.virginia.edu/
Internal, Serious, Unexpected adverse event	IRB-HSR	Within 7 calendar days from the time the study team received knowledge of the event. Timeline includes submission of signed hardcopy of AE form.	IRB Online www.irb.virginia.edu/
For Device Studies: Unanticipated adverse device effects (internal)	IRB-HSR	Within 10 day calendar days of the study team receiving knowledge of the event	IRB Online www.irb.virginia.edu/
Unanticipated Problems that are not adverse events or protocol violations This would include a Data Breach.	IRB-HSR	Within 10 day calendar days of the study team receiving knowledge of the event	IRB Online www.irb.virginia.edu/

CLINICAL PROTOCOL

Protocol Violations/Noncompliance The IRB-HSR only requires that MAJOR violation be reported, unless otherwise required by the sponsor OR Enrollment Exceptions	IRB-HSR	Within 7 calendar days from the time the study team received knowledge of the event.	Unanticipated Problem report form. http://www.virginia.edu/vprgs/irb/HSR_docs/Forms/Reporting_Requirements-Unanticipated_Problems.doc
Data Breach	IRB-HSR	Within 7 calendar days from the time the study team received knowledge of the event.	Protocol Violation, Noncompliance and Enrollment Exception Reporting Form http://www.virginia.edu/vprgs/irb/hsr_forms.html Go to 3 rd bullet from the bottom

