Data Breach	The UVa Corporate Compliance and Privacy Office, a ITC: if breach involves electronic data- Police if breach includes items that are stolen: Stolen on UVA Grounds OR Stolen off UVa Grounds- contact police department of jurisdiction of last known location of PHI	As soon as possible and no later than 24 hours from the time the incident is identified. As soon as possible and no later than 24 hours from the time the incident is identified. IMMEDIATELY.	UVa Corporate Compliance and Privacy Office- [contact] ITC: Information Security Incident Reporting procedure , http://www.itc.virginia.edu/security/reporting.html UVa Police- Phone- [contact]
UVa PI HELD IDE			
Life-threatening and/or fatal unexpected events related or possibly related to the use of the investigational agent.	FDA	Within 7 calendar days of the study team learning of the event	Form FDA 3500A (MedWatch) or narrative

CLINICAL PROTOCOL

Serious, unexpected and related or possibly related adverse events	FDA	Within 15 calendar days after the study team receives knowledge of the event	Form FDA 3500A (MedWatch) or narrative
Unanticipated adverse device effects (internal or external)	FDA	Within 10 working days of the study team receiving knowledge of the event	Form FDA 3500A (MedWatch) or narrative
All adverse events	FDA	Annually	IDE annual report

Table 2: Adverse Events, Unanticipated Problems, Protocol Violations and Data Breaches

Definition of Adverse Event: A reportable adverse event is any untoward medical occurrence or any unexpected medical occurrence in a study subject.

Hypoglycemic events are recorded as Adverse Events if the event required assistance of another person due to altered consciousness to actively administer carbohydrate, glucagon, or other resuscitative actions. This means that the subject was impaired cognitively to the point that he/she was unable to treat him or herself, was unable to verbalize his or her needs, was incoherent, disoriented, and/or combative, or experienced seizure or coma. These episodes may be associated with sufficient neuroglycopenia to induce seizure or coma. If plasma glucose measurements are not available during such an event, neurological recovery attributable to the restoration of plasma glucose to normal is considered sufficient evidence that the event was induced by a low plasma glucose concentration.

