Hyperglycemic events are recorded as Adverse Events if evaluation or treatment was obtained from a health care provider or if the event involved diabetic ketoacidosis (DKA), as defined by the Diabetes Control and Complications Trial (DCCT), and had all of the following:

- Symptoms such as polyuria, polydipsia, nausea, or vomiting;
- Serum ketones or large/moderate urine ketones;
- Either arterial blood pH <7.30 or venous pH <7.24 or serum bicarbonate <15; and
- Treatment provided in a health care facility

Recording of Adverse Events: Throughout the course of the study, all efforts will be made to remain alert to possible adverse events or untoward findings. The first concern will be the safety of the subject, and appropriate medical intervention will be made.

The investigator will elicit reports of adverse events from the subject at each visit and

complete all adverse event forms.

The investigator will assess the relationship of any adverse event to be related or unrelated by determining if there is a reasonable possibility that the adverse event may have been caused by the study device or study procedures.

The intensity of adverse events will be rated on a three-point scale: (1) mild, (2) moderate, or (3) severe. It is emphasized that the term severe is a measure of intensity: thus a severe adverse event is not necessarily serious. For example, itching for several days may be rated as severe, but may not be clinically serious.

Adverse events that continue after the participant's discontinuation or completion of the study will be followed until their medical outcome is determined or until no further change in the condition is expected.

Adverse events will be coded using the MedDRA dictionary.

Definitions of relationship and intensity are listed on the data entry form.

Reporting Serious or Unexpected Adverse Events

A **serious adverse** event is any untoward occurrence that:

- results in death,
- is life-threatening (a non-life-threatening event which, had it been more severe, might have become life-threatening, is not necessarily considered a serious adverse event),
- requires inpatient hospitalization or prolongation of existing hospitalization,
- results in significant disability/incapacity, or
- is a congenital anomaly/birth defect

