The PI will conduct an aggregate review of the following data:

- ❖ All adverse events
- ❖ Unanticipated Problems
- ❖ Protocol violations
- ❖ Audit results

- ❖ Early withdrawals
- ❖ Data processing review

IRB-HSR will be updated annually on the IRB-HSR continuation status form. This annual report will address:

- ❖ Brief summary of research progress
- ❖ Whether adverse event rates are consistent with pre-study assumptions
- ❖ Enrollment status
- ❖ Reason for dropouts from the study
- ❖ Whether continuation of the study is justified
- ❖ Conditions whereby the study might be terminated prematurely

The relevant device regulation for reporting adverse events to the FDA will also be followed.

Data from each subject will be reviewed by the PI after completion of participation to determine whether the DiAs system was working properly and whether there were safety concerns.

Adverse Events / Unanticipated Problems

Recording, Reporting, and Grading

Only adverse events that are deemed related AND serious will be recorded, reported, and graded. The principal investigator will be responsible for the overall safety monitoring of the study. The principal investigator, along with the sub-investigators, will review the individual adverse events as they occur. Any event that merits adverse event reporting will be collected and recorded in the IRB database by completing the IRB Adverse Event Reporting form online. The principal investigator can then use this database to produce a report of all adverse events reported on the study to do an aggregate review. If the AE is unexpected and serious, a signed hard copy of the IRB Adverse Event Reporting form will be submitted to the IRB within 7 calendar days.

Grading of Adverse Events

- ❖ Mild/Moderate/Severe
- ❖ Serious/Not serious

The PI will determine the relationship of adverse events to the study using the following scale:

- ❖ Related: AE is clearly related to the intervention
- ❖ Possibly related: AE may be related to the intervention
- ❖ Unrelated: AE is clearly not related to intervention

Reporting/recording of adverse events/unanticipated problems will begin after the subject begins study drug/device placement/intervention/study-related procedure/specimen collection.

Reporting/recording of adverse events/unanticipated problems will end at the end of study drug/device/ intervention/participation.

CATASTROPHIC EVENT PLAN

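### The rule limiting adverse event recording to related and serious events contradicts the protocol's other adverse event rules and, followed literally, leaves non-serious and unrelated events unrecorded

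*Combined protocol and SAP*

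**What the plan says.** The restrictive rule stands under Adverse Events / Unanticipated Problems, in Recording, Reporting, and Grading: "Only adverse events that are deemed related AND serious will be recorded, reported, and graded". It covers three acts at once and names no recipient, form or database.

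The rest of the safety section is wider:

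- **Table 2, IRB rows.** One row reads "Internal, Serious, Unexpected adverse event", due within 7 calendar days. It sets no relatedness condition.
- **Table 2, FDA rows.** "All adverse events" go to the FDA annually in the IDE report.
- **Definition of Adverse Event.** "A reportable adverse event is any untoward medical occurrence or any unexpected medical occurrence in a study subject". For low glucose: "Hypoglycemic events are recorded as Adverse Events if the event required assistance of another person due to altered consciousness". For high glucose: "Hyperglycemic events are recorded as Adverse Events if evaluation or treatment was obtained from a health care provider", with DKA as an alternative trigger.
- **Recording of Adverse Events.** "The investigator will elicit reports of adverse events from the subject at each visit" and complete all the forms. Relationship is assessed for any event, and intensity is rated with a deliberately non-serious illustration: "itching for several days may be rated as severe, but may not be clinically serious".
- **Reporting Serious or Unexpected Adverse Events.** All anticipated events are to be reported to both the IRB and the FDA within 3 months of trial completion.
- **Grading of Adverse Events.** The categories include *Not serious*, *Possibly related* and *Unrelated*.

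**The concern.** Site staff cannot obey both sets of instructions. If they follow the restrictive sentence, events that the definitions require to be recorded never enter the record. If they follow the definitions, they breach the restrictive sentence.

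At stake is the completeness of the record used for three purposes: the principal investigator's aggregate review, the annual IRB statement on whether adverse event rates match pre-study assumptions, and the FDA annual report. The sentence is also hard to apply on its own terms, because the protocol gives two different tests of what counts as related.

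**Working it through.** No figure in the plan bears on this, so there is nothing to recompute. The check is to take events that the other rules clearly cover and ask whether the restrictive sentence admits them. It admits an event only if it is both serious and related.

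**Step 1: the seriousness test.** The protocol lists five criteria: death, threat to life, hospitalization or its prolongation, significant disability, and congenital anomaly. Needing another person's help, or being seen by a provider, is not among them.

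**Step 2: events set against the rules.**

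| Event | What the other rules require | Under the restrictive sentence |
|---|---|---|
| Hypoglycemia with disorientation, carbohydrate given by another person, no seizure, none of the five criteria met | Recorded (Definition of Adverse Event) | Excluded: not serious |
| Hyperglycemia evaluated by a provider, none of the five criteria met | Recorded (Definition of Adverse Event) | Excluded: not serious |
| Itching over several days, not serious | Rated for intensity (Recording of Adverse Events) | Excluded: not serious |
| Serious, unexpected event judged unrelated | To the IRB within 7 calendar days (Table 2) | Excluded: not related |
| Anticipated event, not serious | To the IRB and FDA after completion (Reporting Serious or Unexpected Adverse Events) | Excluded: not serious |
| Any event that is non-serious or unrelated | To the FDA annually (Table 2) | Excluded |

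The first row leaves out seizure because the criteria for stopping an individual subject give hypoglycemic seizure as an example of a serious event.

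**Step 3: consistency within the same part of the protocol.** If only related and serious events were graded, the *Not serious* and *Unrelated* categories could never be used.

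**Step 4: what related means.** Recording of Adverse Events uses two levels, with a reasonable-possibility threshold. Grading of Adverse Events uses three, and reserves *Related* for events clearly due to the intervention. A serious event judged *Possibly related* could pass the filter under the first scale and fail under the second. Table 2's expedited FDA rows explicitly take in possibly related events. This ambiguity is secondary: non-serious and unrelated events are excluded on either scale.

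**The case against.** The best defense is that the sentence was meant only for the IRB online form. There is support for it. The same paragraph says that events meriting adverse event reporting are entered in the IRB database through that form. The preceding reporting section gives the principal investigator a duty to inform the IRB of serious study-related events. The text just before the sentence says that device regulations for FDA reporting will also be followed. Recording of Adverse Events also points to a separate study record, with its own forms, MedDRA coding and a data entry form. Staff may therefore record more in practice than the sentence allows, and this part of the defense stands.

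It does not rescue the text, for three reasons. The sentence limits recording and grading as well as reporting, and names no route. Table 2's IRB row still conflicts, because it has no relatedness condition. And the same paragraph says that the investigator can use that database for the aggregate review, so an IRB-only filter would still narrow a source named for safety oversight.

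Some of the apparent contradictions are weaker than they look:

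- The later sentence on unexpected and serious events largely repeats the Table 2 row. It can also be read as a further step for events already admitted, so it should not be counted as a separate conflict.
- The report of anticipated events is an end-of-study report. On an IRB-form reading it could be a different route.
- The item listing all adverse events for the aggregate review could mean all those reported.

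**Conclusion.** The contradiction is real and the text should be corrected. The restrictive sentence conflicts with Table 2, the adverse event definitions, the recording rules, the report of anticipated events and the protocol's own grades. Read literally, it leaves unrecorded all non-serious events and all serious events judged unrelated.

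The size cannot be given: the documents contain no expected event counts, and nothing shows which instruction staff actually followed. The conclusion assumes only that the sentence means what it says; the IRB-form reading narrows the conflict but does not end it.

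A reader might infer more than the documents support:

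- **That the trial's main safety conclusion is at risk.** It is not affected by this point. The success criterion is defined by LBGI from CGM data, and the statistical analysis plan contains no adverse event analysis. The harm is to safety oversight and to IRB and FDA reporting.
- **That the whole-study stopping rule would fail.** That rule counts similar events that stopped individual subjects, and no text ties the count to adverse event forms. Staff would know of such stops directly.
- **That safety review is absent.** Individual events are reviewed as they occur, each subject's data are reviewed after completion, and early withdrawals are part of the aggregate review.

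**What to change.** 1. Delete the restrictive sentence, or confine it to a named IRB reporting route whose conditions agree with Table 2's serious-unexpected row and with the end-of-study report of anticipated events.
2. State once that all adverse events meeting the protocol's definitions, including its hypoglycemia and hyperglycemia rules, are recorded and graded for seriousness, intensity and relatedness.
3. Replace the two-level and three-level relatedness scales with a single scale, and say how possibly related events are treated in each reporting route.

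The cost is protocol wording and some additional forms, a number that the documents do not allow to be estimated. Events are already to be elicited at each visit, so no new contact with subjects is needed.

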Visit 3: Data Collection Period. Blinded CGM data will be collected prior to the Experimental admission and analyzed by the study team to determine the optimal insulin therapy parameters that will be used during the Experimental admission. For CSII users, the insulin pump and CGM downloads will be reviewed approximately 72 hours before the Experimental admission by the study team to ensure proper collection procedures. For MDI users, data entered into the MySugr app and CGM downloads will be similarly reviewed. Subjects will also wear a 'Fitbit' to collect information activity, exercise, heart rate, and sleep. An anonymous Gmail account will be established for each subject. An app will be placed on the subject's smartphone or subject's personal laptop to facilitate weekly downloading of the Fitbit data. Additional Data Collection Periods may be requested to ensure proper data collection.

Visit 4 and 5: Research House/Hotel Admission. The Experimental and Control admission will be separated by approximately 4 weeks, 8 weeks or 12 weeks. The order of these two visits will be randomly selected. Subjects will be admitted to the research house/hotel at ~16:00-17:00 and will be discharged after approximately 48 hours.

Figure 1: Study Design

C. Sample Size and Investigational Sites

This study will be conducted at the University of Virginia Center for Diabetes Technology (CDT). Twenty subjects (N=20) with Type 1 Diabetes Mellitus who use CSII and twenty subjects (N=20) with Type 1 Diabetes Mellitus who use MDI to treat their diabetes will be needed to complete the protocol. The studies will be conducted at the CDT Research House as noted below. The study may also occur at a local hotel. Vulnerable populations (i.e. pregnant women, prisoners, etc.) will be excluded from participation. Based on our experience with similar studies, we estimate an higher than normal screen failures, dropouts, or withdrawals due to the data collection requirements and admission time restrictions; thus we intend to set a recruiting target of 70 subjects.

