5. The study team will confirm that the subject brought his/her insulin, insulin pump or MDI supplies, and regular medications. The study team will also confirm the absence of a febrile illness and absence of acetaminophen use while wearing the CGM sensor. The subject may be rescheduled if these criteria are not met.
6. Female subjects of childbearing potential will perform a urine pregnancy test. If positive, the subject will discontinue study participation. The subject will be asked to seek confirmation of the test and the appropriate medical care.

Admission Procedures

Day 1

1. **General Information:** During both admissions, the subject will wear a blinded Dexcom CGM connected to DiAs for remote monitoring capabilities. The staff will remotely monitor the subject using the remote monitoring website. DiAs will be programmed with the home insulin dosing parameters during the Control admission and with the optimized insulin dosing parameters during the Experimental condition. DiAs will be used for meal insulin dosing advice for both admissions and for pre-exercise advice during the Experimental admission. DiAs will be informed of any BG values, meals, carb treatments, correction doses, or snacks during the admission. The DiAs system will be initiated prior to dinner.
 - a. **Experimental Admission** – The DiAs will be programmed with the new optimized basal rates or basal insulin dose (entered as a basal rate U/hr = Lantus, Tresiba, Levemir dose/24hr), insulin sensitivity factor(s), and carbohydrate ratio(s). These new parameters will be used for insulin dosing advice during the entire admission. MDI users will use the study insulin pen for meal insulin dosing and the home insulin pen or syringe for Lantus (glargine), Tresiba [degludec], or Levemir [Detemir] dosing. Pump users will use the home pump for both meal insulin dosing and basal insulin administration during the admission.
 - b. **Control Admission** – The study subject will use the home basal/bolus MDI or CSII insulin regimen via the home insulin pens or pump and determine the amount of insulin to give for the entire admission per the subject's home carb counting parameters and as calculated by the DiAs meal screen.

2. **Dinner:** A dinner meal will be provided between 18:00-19:00. The subject will define the amount of carbohydrates at the dinner meal. The amount of carbs designated by the subject will be consistent between the Control and Experimental admission.

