The subject will be introduced to the blinded CGM by a qualified member of the study team. The subject will be instructed how the device is inserted, calibrated and removed. The subject will be trained how to upload the CGM data. The subject will verbalize understanding of how the device is used, how to insert the device, how to calibrate the device and how to remove the device. The subject, with the guidance of the study team, will then insert the sensor and begin wearing the CGM. The study team will teach the subject how to calibrate the device as needed. The study team will confirm that all questions have been answered and that the subject has understood the training. The subject will be given a contact sheet containing phone numbers for the study team to call with any questions 24 hours per day.

Study Glucometer Training:

The Bayer CONTOUR NEXT Blood Glucose Monitoring System will be used during visit 2-5 as the study glucometer. The subject will be trained on proper use of the meter as described in the user manual. The subject will then be required to demonstrate proficiency on the use of the device. The subject will be instructed to wash their skin with warm water and a clean towel prior to obtaining fingerstick values. The subject will be instructed to obtain a fingerstick, avoiding alternative sites, when obtaining blood values. The first drop will be discarded. The second hanging drop will be used to measure the glucose level. QC will be completed prior to the subject receiving the study glucometer. The study team will confirm that all questions have been answered and that the subject has understood the training.

DiAs Training:

During the Control and Experimental admissions, a brief introduction to the DiAs UI will occur with a qualified clinical member of the study team. DiAs will be used as an insulin-dosing calculator for both admissions and the advice recommended by DiAs will be instituted using the home insulin pump for CSII users or the study insulin pen (Experimental admission) or home insulin pen (Control admission) for MDI users. For the Control admission, DiAs will be pre-programmed by the study team with the subject's home insulin parameters. For the Experimental admission, DiAs will be pre-programmed with the optimized insulin parameters per the decision support system and that have been approved by the study physician. To minimize risk associated with the use of DiAs:

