The Outpatient Emergency Plan will go into effect should a catastrophic event occur during the study admissions. A catastrophic event is defined as any event that requires emergency treatment by medical professionals that exceed the expected parameters of the protocol. A copy of this plan will be located at the monitoring desk. Staff will be aware of its location at all times.

In the unlikely event of a disruption in 911 phone service, the sites will contact their local non-emergency number (e.g. Charlottesville-UVA-Albemarle Emergency Communications Center can be reached via their non-emergency number [contact]). This number feeds into their main call area where 911 dispatchers are available 24/7.

Event	RN Response	Tech Response
Respiratory Arrest	1) Tell Tech to call 911 2) Begin Basic Life Support	Refer to Study Physician
Cardiac Arrest	1) Tell Tech to call 911 2) Begin Basic Life Support	Refer to Study Physician
Severe Hypoglycemic Event as defined by hypoglycemia accompanied by unconsciousness or seizure	1) Tell Tech to call 911 2) Administer glucagon IM (described in Glycemic Treatment Guidelines Appendix A-6) 3) Remove study pump	Refer to Study Physician
Severe Hyperglycemic Event as defined by β -ketone level ≥ 3.0 mmol/L	1) Discuss correction dose of insulin to administer s.c. via syringe with study M.D. 2) Encourage P.O. water intake 3) Remove study pump and start home insulin pump 4) Go to nearest medical facility for evaluation and treatment.	Refer to Study Physician

Table 3: Outpatient Emergency Plan

ENDPOINTS

We assess the risk to the subject by computing the two classical hypo and hyperglycemia risk indices LBGI and HBGI, based of the blinded CGM data, retrofitted to the SMBG point (see DelFavero et al. JDST 2015). Gaps of less than 3h will be filled using spline based interpolation. LBGI is the primary endpoint.

LBGI and HBGI are measures of glycemic risk that were developed by our groups in the late 1990s and have been shown to be predictive of increased frequency of severe hypoglycemia and increased HbA1c. Detailed formula can be found in Kovatchev et al. Diabetes Care 1998.

In addition we will capture:

- Quality of glycemic control using the percent time spent between 70mg/dl and 180mg/dl.
- Meal insulin coverage will be assessed using Area Under the glucose Curve in the postprandial state.

CLINICAL PROTOCOL

- Glucose variability will be assessed using the Risk Index (sum of LBGI and HBGI).

SUCCESS CRITERIA / GOAL

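### Table 3's severe hyperglycemia step assumes two pumps, which no subject has, and its severe hypoglycemia step does not make clear which pump is meant

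*Combined protocol and SAP*

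**What the plan says.** The Catastrophic Event Plan sets the scope of the table: "The Outpatient Emergency Plan will go into effect should a catastrophic event occur during the study admissions". It therefore covers both the Control and the Experimental admission, and a copy is kept at the monitoring desk.

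Two of the four rows of Table 3 mention a pump. For severe hypoglycemia (unconsciousness or seizure), the nurse's last step is "3) Remove study pump". For severe hyperglycemia (β-ketone at or above 3.0 mmol/L), the third of four steps is "Remove study pump and start home insulin pump".

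The devices are assigned in Admission Procedures, Day 1, item 1:

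- CSII, Experimental: "Pump users will use the home pump for both meal insulin dosing and basal insulin administration during the admission".
- CSII and MDI, Control: "The study subject will use the home basal/bolus MDI or CSII insulin regimen via the home insulin pens or pump".
- MDI, Experimental: "MDI users will use the study insulin pen for meal insulin dosing and the home insulin pen or syringe for Lantus" or the other permitted basal insulins.

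The DiAs Training text under Misuse Risk says the same again. The advice from DiAs is carried out "using the home insulin pump for CSII users or the study insulin pen (Experimental admission) or home insulin pen (Control admission) for MDI users".

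**The concern.** Table 3 is operative text, to be used under time pressure when a subject is unconscious, seizing or markedly ketotic. Its hyperglycemia row treats the study pump and the home pump as two devices, one to come off and the other to go on. The sections that say what subjects wear describe no such pair.

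A nurse attending a CSII subject with severe hypoglycemia could take the pump step to mean the pump being worn. The nurse could equally pass over it, on the ground that the study has supplied no pump. These are different actions on a device that may be delivering insulin, and the table does not say which is meant. What is at stake is clear emergency instructions. Randomization, the endpoint and the analysis are not involved.

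**Working it through.** No figure in the plan bears on this point, so the check sets the passages side by side.

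**Step 1: which device is in use in each group and admission?** The sources are Admission Procedures, Day 1, item 1, and DiAs Training.

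| Group | Experimental admission | Control admission |
|---|---|---|
| CSII | home pump, bolus and basal | home pump |
| MDI | study pen for meals; home pen or syringe for basal | home pens |

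A separate study pump appears in 0 of the 4 cells. The only dosing device that the study supplies is the MDI pen.

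**Step 2: does any other section supply a study pump?** None was found. The training text under Misuse Risk covers the CGM, the glucometer and DiAs. The Device Reuse Risk text covers the CGM, glucometers and insulin pens. Neither mentions a pump issued by the study.

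Two sections bear on what the term could mean:

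- Equipment Specifications, item 1, includes an insulin pump, for CSII subjects only, in its list of study equipment to be clock-set.
- Visit 2, Continuous Glucose Monitor Training, item 3, describes clock-setting too and attributes the pump to the subject.

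**Step 3: try each meaning of the term against each row.**

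| Meaning of study pump | Hypoglycemia row | Hyperglycemia row |
|---|---|---|
| A separate pump supplied by the study | nothing to remove | nothing to remove; a CSII subject is already on the home pump |
| The pump the CSII subject is wearing | can be carried out for CSII | remove the home pump, then start the home pump |
| Either meaning, MDI subject | no pump worn | no pump to remove or to start |

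The second meaning makes the hypoglycemia row workable for CSII subjects. It turns the hyperglycemia row into an instruction to take off and start the same device. No single meaning makes both rows fit the device assignments.

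**Step 4: size.** Two of four rows name a study pump. Section C plans 20 CSII completers, and "twenty subjects (N=20) with Type 1 Diabetes Mellitus who use MDI to treat their diabetes will be needed to complete the protocol". MDI subjects are thus 20 / (20 + 20) = 50% of planned completers, and for them neither pump step applies.

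**The case against.** The strongest reply is that the protocol uses the term loosely. Equipment Specifications counts the CSII pump as study equipment, and Procedures Related to Discharge has study equipment removed before the subject resumes home therapy. On that usage the study pump is whichever pump is worn during the admission, and the hypoglycemia step can be carried out for CSII subjects. This stands as a possible reading, so that step is ambiguous and not impossible. The Visit 2 text, which calls the pump the subject's own, keeps it from being settled. The reading does not rescue the hyperglycemia row, which names two pumps.

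The second reply is that the safeguards do not depend on the pump wording, and this also stands. In the hypoglycemia row, the emergency call and glucagon come first. In the hyperglycemia row, a physician-discussed correction dose by syringe comes first, and evaluation at a medical facility is also listed. The technician refers to the study physician in both rows. Minimal Staffing Requirements puts a nurse on site and a physician on call throughout.

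The third reply is that Appendix A-6 may say what to do with the pump. The hypoglycemia row points to it for glucagon, and the Hypoglycemic/Hyperglycemic Risk text applies it at Visits 4 and 5. It is not in the text available for this review. A reader might infer that staff have no instruction at all for the pump a subject is wearing. The documents do not support that: the gap is shown for Table 3 only.

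**Conclusion.** Wrong as written: this is an internal contradiction in operational safety text. It is firm for the severe hyperglycemia row, whose pump step cannot be carried out as written for any subject. In the severe hypoglycemia row, the pump step is ambiguous for CSII subjects and not applicable to MDI subjects.

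Two stronger readings should be set aside. One is that both pump steps are impossible for everyone, which the Equipment Specifications list does not allow. The other is that every planned admission is affected. With 40 completers and 2 admissions each, 40 × 2 = 80 counts the admissions in which the table is in force. The wording comes into play only if a subject loses consciousness, has a seizure or reaches the ketone threshold. The documents give no expected rate for these events, so the number of admissions affected cannot be estimated.

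The conclusion assumes that the device assignments under Admission Procedures and DiAs Training are the intended ones, and it makes no claim about Appendix A-6. It has no bearing on the sample size or the LBGI comparison.

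**What to change.** Reconcile Table 3 with Admission Procedures (Day 1, item 1), DiAs Training, Equipment Specifications (item 1) and the Visit 2 clock-setting step. Each pump-related step should name the device in use, separately for CSII and for MDI subjects. Use one term for the CSII subject's pump throughout, and check Appendix A-6 for the same wording. What is done with that device in each event is a clinical matter for the study physicians, and nothing is proposed here. Then replace the copy at the monitoring desk.

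The cost is the correction of one table, a wording check in the sections named and one reprinted page. No data collection, endpoint or analysis changes.
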